TREATMENT PERCEPTIONS QUESTIONNAIRE: Subjective financial burden assessment – which includes questions assessing stress, anxiety, and guilt related to cancer treatment costs as well as prioritization of treatment costs in the list of disease-related concerns.

CAREGIVER QUESTIONNAIRE: (Consented caregiver only.) Assessment of financial changes made to accommodate patient's cancer treatment expenses and subjective caregiver burden assessment (adapted Caregiver Strain Index), which will include questions assessing stress and anxiety related to patient's cancer treatment costs as well as prioritization of treatment costs in the list of disease-related concerns.

6.5 Performance Status:

Patients will be graded according to the Zubrod Performance Status Scale.

POINT DESCRIPTION

- 0 Fully active, able to carry on all pre-disease performance without restriction.
- 1 Restricted in physically strenuous activity but ambulatory and able to carry out work of a light or sedentary nature, e.g., light housework, office work.
- Ambulatory and capable of self-care but unable to carry out any work activities; up and about more than 50% of waking hours.
- 3 Capable of limited self-care, confined to bed or chair more than 50% of waking hours.
- 4 Completely disabled; cannot carry on any self-care; totally confined to bed or chair,

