7.2 Secondary Objectives

Risk Factors for Financial Hardship

Sample size calculation will be driven by the key secondary objective of this study, which is to assess whether major financial hardship at one year differs by age (< 65 vs. \geq 65), race (white vs. non-white), marital status (married vs. unmarried), employment status (any employment vs. unemployed), and income (household income < \$50,000 / year vs. \geq \$50,000 / year). In particular, we hypothesize that financial hardships are more likely in patients who, at diagnosis, are younger, non-white, unmarried, unemployed, or have lower incomes.

With a series of 5 hypotheses to be tested, we account for multiple comparisons using a conservative Bonferroni alpha = 0.01 two-sided test for each comparison. Three years of accrual with one year of follow-up is anticipated. Based on a two-sample survival design accounting for the competing risk of death (40% deaths at 1 year [hazard rate of 0.51]), n=320 eligible, evaluable patients will give 90% power to detect an absolute difference of 20% (that is, 30% rate at year 1 in good performing group [hazard rate 0.356] vs. 50% in poor performing group [hazard rate of 0.693]) in the proportion of patients with major financial hardship, if a ratio of patients between two groups is 1:1. This corresponds to a hazard ratio of 1.95. Power drops to 83% if the ratio of patients in subgroups is 2:1.

The effect of age, race, marital status, employment status, and income on major financial hardship will be estimated using multivariable Cox regression. The regression will include the 5 covariates of interest plus insurance status, education, and gender. A sample size of 320 eligible patients ensures that the ratio of events to independent predictors will be at least 10:1. (22, 23)

Major Financial Hardship and HRQOL:

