A secondary objective of this study is to assess the relationship between major financial hardship and HRQOL. These factors are likely positively correlated and associated with the same general status of poor prognosis (endogenous factors). analysis that evaluates, from baseline, the association of major financial hardship and HRQOL will find a positive correlation as an artifact of the endogeneity, and adjustment for performance status is unlikely to fully account for this. Therefore we will use landmark analysis to establish major financial hardship as a baseline predictor of HRQOL. In particular, patients will be categorized as having major financial hardship at their 3 month assessment (yes vs. no). We will then use linear regression to assess whether the 3month assessment of financial hardship predicts the 6-month HRQOL score. HRQOL at 3 months will be included as an adjustment covariate. The 6-month HRQOL score will be based on the EORTC QLQ-C30 questionnaire transformed into a linear score (0 to 100) using the EORTC scoring manual. A difference in mean score of ≥ 10 between time points is considered clinically relevant. In addition, to assess the robustness of potential associations between major financial hardship and HRQOL to large changes in a subset of patients, HRQOL at 6 months will also be categorized as decline vs. no decline and logistic regression performed. This analysis is limited by the fact that patients without 6 months follow-up scores are more likely to be worse prognosis patients that may also be related to predictive factors of interest (that is, age, race, marital status, employment status, and income).

Feasibility

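### The Section 7.2 Cox model has no term for performance status, so sickness at entry can be partly read as an effect of employment status

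*Combined protocol and SAP*

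**What the plan says.** Section 7.2 (Risk Factors for Financial Hardship) states: "The effect of age, race, marital status, employment status, and income on major financial hardship will be estimated using multivariable Cox regression". It then lists the model: "The regression will include the 5 covariates of interest plus insurance status, education, and gender". That makes eight covariates, none of them clinical, and no sensitivity analysis adds one. The employment contrast is "employment status (any employment vs. unemployed"). Unemployed patients are hypothesised to have more hardship, and each of the five comparisons is tested at a two-sided 0.01.

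Section 6.5 says: "Patients will be graded according to the Zubrod Performance Status Scale". The grade between 1 and 3 reads: "Ambulatory and capable of self-care but unable to carry out any work activities". The section gives neither a time point nor a form for the grading. The study calendar (5.0) and the submission list (9.4) name no separate performance status item.

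The quality-of-life part of Section 7.2 says of hardship and quality of life: "These factors are likely positively correlated and associated with the same general status of poor prognosis (endogenous factors"). It expects those who lack a 6-month score to fall more often into this group: "worse prognosis patients that may also be related to predictive factors of interest (that is, age, race, marital status, employment status, and income"). Performance status is mentioned only here, with the remark that "adjustment for performance status is unlikely to fully account for this".

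Objective 1.2a is more modest than Section 7.2. It asks for a description of association, not an effect.

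**The concern.** The plan names both links of a confounding path: prognosis with hardship, and prognosis with employment status. For the quality-of-life analysis it responds with a landmark design adjusted for 3-month quality of life. The risk-factor model, for which Section 7.2 says the sample size was chosen, has no counterpart.

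The timing makes the path plausible. The hypotheses refer to status at diagnosis, but Section 3.1 allows registration up to 120 days after diagnosis and up to 60 days after systemic therapy began. Illness may already have ended someone's employment by the baseline questionnaire. Confounding of this kind pushes the employment estimate in the hypothesised direction. At stake is whether a positive employment result can be read as something about work or income protection, or only as a sign that sicker patients fare worse financially.

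**Working it through.** **1. The plan's own figure.** Inputs from Section 7.2: n = 320, hardship hazards 0.356 and 0.693, death hazard 0.51, hazard ratio (HR) 1.95, two-sided alpha 0.01, three years of accrual plus one year of follow-up. Cumulative incidence by time t is h/(h+d) × (1 − exp(−(h+d)t)). Averaged over uniform accrual with 1 to 4 years of follow-up, this gives 140.6 events at 1:1. Power = Φ(√(140.6/4) × ln 1.95 − 2.576) = Φ(3.959 − 2.576) = 0.917, against the stated 90%. At 2:1, with one third in the poor group, 131.0 events give 0.848, against 83%. Both agree within two points.

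**2. Size of the possible bias.** Every performance status input here is an assumption, because the documents give none. Set-up: true employment HR 1.0, half the patients unemployed, 12 months of follow-up, hardship and death hazards of 0.40 in patients with good status, death hazard 2.5 times higher with poor status. Each scenario was fitted to 200,000 simulated patients. The rejection rate at nominal 0.01 uses Φ(−2.576 + b√(E/4)) + Φ(−2.576 − b√(E/4)), where b is the log of the spurious HR and E is 320 times the event rate.

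| Poor status, employed vs unemployed | Hardship HR of poor status | Employment HR, status omitted | Rejection at nominal 0.01 |
|---|---|---|---|
| 5% vs 15% | 1.5 | 1.027 | 0.011 |
| 5% vs 15% | 2.0 | 1.070 | 0.014 |
| 5% vs 15% | 3.0 | 1.107 | 0.020 |
| 10% vs 30% | 1.5 | 1.087 | 0.016 |
| 10% vs 30% | 2.0 | 1.157 | 0.031 |
| 10% vs 30% | 3.0 | 1.252 | 0.075 |
| 15% vs 45% | 1.5 | 1.110 | 0.020 |
| 15% vs 45% | 2.0 | 1.225 | 0.058 |
| 15% vs 45% | 3.0 | 1.373 | 0.178 |

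Two hand checks on the row 10% vs 30%, HR 2.0:
- At time zero the spurious ratio is (1 + 0.30 × 1)/(1 + 0.10 × 1) = 1.30/1.10 = 1.18. It falls slightly as high-risk patients leave the risk set, which fits 1.157.
- With event rate 0.295, E = 94.4 and b = 0.146, so b√(E/4) = 0.708 and the rejection rate is Φ(−1.868) + Φ(−3.284) ≈ 0.031.

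With performance status in the model, the employment HR returns to 0.99-1.01 in every scenario.

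A second simulation used n = 320, hazards 0.511 and 0.51, and 2,000 runs per scenario. Poor status was assumed in 5% of employed and 25-35% of unemployed patients, with HR 1.5-2.0 for hardship and 2.0 for death. The employment HR was 1.08-1.23 without the term and 0.99-1.01 with it. The standard error of the log HR rose from 0.200 to 0.210 in the mildest scenario (5%) and from 0.202 to 0.223 in the strongest (10%).

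**3. Room for one more term.** The cautious event count stops follow-up at 12 months (Section 4.9) with competing deaths. The cumulative incidences are 0.238 and 0.403, with mean 0.321, so 320 × 0.321 ≈ 103 events. Events per predictor go from 103/8 = 12.9 to 103/9 = 11.4. At a crude 40% incidence they go from 128/8 = 16.0 to 128/9 = 14.2. These counts give each covariate one parameter. If insurance and education each take three levels, the model has 10 parameters, or 11 with performance status, and 103/11 = 9.4. Adding 10% dropout as a hazard of 0.105 gives about 98 events and 98/11 = 8.9. Even without the new term that coding gives 98/10 = 9.8.

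**The case against.** The strongest reply is that objective 1.2a asks only for a description of association. An unemployed patient who is also sicker is still at higher risk, and for finding who needs help the stated model answers the question. This stands, and it is why the stated model should remain. It does not cover Section 7.2, which speaks of effects and already adjusts for insurance, education and gender.

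Second, one model serves all five factors, and performance status may lie downstream of age, race and income. Adding it to the only model could remove part of what the objective asks for. This also stands, and it argues for a second model instead of a replacement.

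Third, the plan doubts that adjusting for performance status would be enough. That remark concerns quality of life, where another remedy was adopted. Incomplete control is a reason for caution in reading the result, not for having no control.

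Fourth, the bias sizes are assumed, and Section 3.1 requires planned or started systemic therapy, which may keep poor status uncommon. This stands; the low end of the range is close to no bias.

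Three stronger readings are tempting, and the documents do not support them:
- **The 0.01 level is not held.** The excess rejections are errors only under a null of no employment effect independent of health. Under a null of no association given the listed covariates they are correct findings, and their frequency depends on assumed inputs.
- **Performance status is tied to employment by definition.** The scale grades capacity to work, while the covariate records employment. A patient on leave may count as employed and a fit retiree as unemployed.
- **The handling of deaths fails.** Section 7.1 treats death as a competing risk. Read as a cause-specific hazard ratio, the Cox estimate does not need deaths to be independent of hardship. At most the omission touches the roughly 10% of non-death dropouts who are censored, and that was not quantified.

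**Conclusion.** The concern holds as a limit on interpretation. The model as written describes how hardship differs by employment status, but it cannot separate employment from sickness at entry, and the plan's own text gives reason to expect the two to be linked. Under the assumed inputs the spurious employment HR runs from about 1.03, with rejection essentially nominal, to about 1.37, when the true independent HR is 1.0. This rests wholly on the assumed prevalences (5-15% of employed, 15-45% of unemployed), the assumed HRs of poor status (1.5-3.0 for hardship, 2.5 for death) and a 1:1 split. Confounding of this size would not by itself produce the design HR of 1.95. It could account for a modest employment association. Adjustment would reduce the confounding and need not remove it.

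**What to change.** Keep the stated eight-covariate model as the descriptive analysis of association, and let it carry the five tests at 0.01. Add to Section 7.2 a pre-specified second Cox model with the same covariates plus baseline Zubrod performance status (0-1 vs 2 or more), and report all five factor estimates from both models. State that the employment estimate is to be read as independent of health only from the adjusted model, and that for age, race and income the adjusted estimate may remove a mediated part. State in Section 6.5 that the baseline grade is recorded at registration, for example on the Onstudy Form. If that form does not hold it, one data item has to be added.

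The cost is one extra model and one degree of freedom, with the 5-10% loss of precision for employment shown above. Events per predictor stay near 11 with a 12-month cap if each covariate takes one parameter. They fall below 10 if insurance and education enter with three or more levels, so the plan should also fix that coding.

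### The 6-month HRQOL landmark model adjusts only for 3-month HRQOL, and the logistic check names no covariate, so measured demographic factors could still confound the hardship–HRQOL association

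*Combined protocol and SAP*

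**What the plan says.** Section 7.2 (Major Financial Hardship and HRQOL) recognizes that hardship and HRQOL share a cause: "These factors are likely positively correlated and associated with the same general status of poor prognosis (endogenous factors". It adds that "adjustment for performance status is unlikely to fully account for this", and therefore starts the analysis at month 3 instead of at baseline. Hardship at the 3-month assessment (yes or no) is the predictor and the 6-month QLQ-C30 score is the outcome. The adjustment is stated in one sentence: "HRQOL at 3 months will be included as an adjustment covariate".

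A second analysis is meant to check robustness to large changes in some patients: "HRQOL at 6 months will also be categorized as decline vs. no decline and logistic regression performed". It names no covariate, and it does not say from when, or by how much, a patient must fall to count as declined. On relevance the section says: "A difference in mean score of ≥ 10 between time points is considered clinically relevant". The one limitation it states concerns patients without a 6-month score.

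Earlier in Section 7.2 (Risk Factors for Financial Hardship) the plan says: "we hypothesize that financial hardships are more likely in patients who, at diagnosis, are younger, non-white, unmarried, unemployed, or have lower incomes". For the Cox model of hardship it says: "The regression will include the 5 covariates of interest plus insurance status, education, and gender". Section 1.2b words the HRQOL objective as exploratory.

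**The concern.** A baseline factor confounds the month-3 hardship coefficient if it is related to hardship by month 3 and also changes HRQOL between months 3 and 6, over and above the 3-month score. The plan supplies the first link: prognosis by its own statement, and five demographic factors as a hypothesis. The preliminary study in Section 2.0 found younger age and income below $50,000 most closely associated with hardship. If the second link exists for any of these factors, a hardship–HRQOL association, or its absence, could partly reflect age, income, employment or prognosis.

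The plan lists eight baseline covariates for the hardship model and one for the HRQOL model. At stake is the interpretation of one exploratory secondary objective.

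**Working it through.** **No plan figure to reproduce.** The documents give no sample size, SD, power or significance level for this analysis. The nearest figure is the Cox design effect. Hazards of 0.693 and 0.356 give 0.693 / 0.356 = 1.947, which agrees with "This corresponds to a hazard ratio of 1.95". That is the detectable difference for one two-group comparison, not an expected effect for every factor. Applied to all five factors it implies a 1.95^5 = 28-fold spread in hazard; 1.3 implies 1.3^5 = 3.7-fold.

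**Size of the analysis set**, from Section 7.1 (320 evaluable, 40% deaths and about 10% other dropout by 1 year, 40% hardship by 1 year, exponential):
- Patients at month 6: 320 × exp(−0.511 × 0.5) × exp(−0.105 × 0.5) = 235, before missed forms.
- Hardship by month 3: 1 − exp(−0.511/4) = 12.0%, or about 28 of 235.

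**Bias from one omitted factor.** At the design hazards, hardship by month 3 is 1 − exp(−0.356/4) = 8.5% against 1 − exp(−0.693/4) = 15.9%. For a factor split 1:1, the poorer group makes up 0.159 / (0.159 + 0.085) = 65% of patients with hardship and 0.841 / (0.841 + 0.915) = 48% of the rest, an imbalance of 0.172. Approximate bias is the later effect times the imbalance: 2, 5 or 10 points give about 0.3, 0.9 or 1.7 points.

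**Illustration A** (true hardship effect zero; all inputs below are assumptions). Prevalences: younger 50%, non-white 20%, unmarried 40%, unemployed 50%, low income 45%, poor prognosis 30%. Every factor has the same hazard ratio for hardship. Poor prognosis lowers the 3-month score by 10. Residual SD is 16. A performance-status proxy is positive in 65% of poor-prognosis patients and 20% of others. Low income and no employment each add 2 or 4 points of later decline. Entries are the false hardship coefficient in the planned model → after adding the five factors and the proxy.

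| Later prognosis effect | HR 1.3, 2 pts | HR 1.3, 4 pts | HR 1.95, 2 pts | HR 1.95, 4 pts |
|---|---|---|---|---|
| 0 | −0.31 → −0.03 | −0.58 → −0.03 | −0.67 → 0.01 | −1.34 → 0.01 |
| 5 | −0.59 → −0.26 | −0.87 → −0.26 | −1.40 → −0.63 | −2.07 → −0.63 |
| 10 | −0.88 → −0.50 | −1.16 → −0.50 | −2.13 → −1.27 | −2.80 → −1.27 |

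Simulation error is about 3.3 × √(235/600,000) = 0.065, so the second decimal carries no meaning.

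- Standard error at n = 235: 3.25 to 3.43. All values lie below it.
- Direction is not fixed. If only age acts (younger patients decline 4 points less), the planned model gives +0.25 (HR 1.3) or +0.66 (HR 1.95).
- If only prognosis acts, adjustment removes 13–19% (for example −1.46 → −1.27). Without a performance-status measure it removes none (−1.46 → −1.55).
- Where age and prognosis nearly cancel (HR 1.95), adjustment moves the estimate away from zero: −0.07 → −0.63.
- Type I error (nominal 5% assumed): planned 4.7–6.5% at HR 1.3 and 4.8–13.6% at HR 1.95; adjusted 4.5–5.8% and 4.8–7.4%.

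**Illustration B** (harsher assumptions). Five 1:1 factors, each at 1.95, each lower HRQOL by 2 or 5 points at month 3 and again by month 6. Residual SD is 12, and about 15% have hardship. The planned model gives −1.7 or −3.7; adding the five factors gives about 0. Prognosis alone gives −0.8 to −2.2, and adding the five factors leaves −0.9 to −2.4. Both together give −2.5 to −5.5 in the planned model. The standard error here is at least about 12 × √(1/35 + 1/200) = 2.2, so the larger values exceed it. All stay below 10.

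**Logistic check** (decline taken as a fall of 10 or more points from month 3, an assumption). In A the false odds ratio with hardship alone was 1.06–1.28 in settings where the demographic and prognosis effects act in the same direction. In B it was 1.17–1.41 from the five factors and 1.26–1.73 with prognosis added. In A 53 to 96 of 235 patients decline. At 10 events per term, 53 events support five terms; hardship, 3-month HRQOL, performance status and five factors are eight terms and would need 80.

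**The case against.** The plan made a reasoned choice: it discusses shared causes, rejects analysis from baseline, and uses a landmark with adjustment for the prior score. That is a recognized design for an exploratory objective. The Cox model has a different outcome and purpose, so its covariate list does not bind the HRQOL model. If decline is measured from month 3, the logistic outcome already uses the 3-month score. All of this stands. A reader might infer that the plan ignored confounding or contradicts itself; the documents do not support either.

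The second link of the demographic path, an effect on HRQOL after month 3, is nowhere in the documents, and even the first is only a hypothesis. The preliminary study reports employment with non-adherence, not with hardship. So it would go too far to say that the five factors drive hardship, or that the planned estimate is materially biased. The size above comes from chosen inputs: A and B differ because their assumptions differ.

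The proposed covariates also barely touch prognosis, the confounder the plan names. That stands too, and the adjusted model should not be presented as a cure for it.

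What the objection does not answer is that performance status being only a partial control is no reason to leave out measured covariates, and that the stated limitation is about missing scores, not about confounding among patients who are observed.

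**Conclusion.** The point holds as a cheap improvement, not as an error in a stated figure. The linear model controls for 3-month HRQOL only, the logistic check names no covariate, and no other section adds any. Measured demographic factors would confound the association if they affect HRQOL after month 3. Whether they do, how strongly and in which direction cannot be learned from the documents.

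Under the moderate assumptions (A) the false difference is below one standard error. It exceeds that in B mainly when all five factors carry the 1.95 hazard ratio and all push HRQOL the same way. It is below 10 points throughout. A reader might infer a high risk of a false finding from the 13.6% type I error; that is the top of the range with 1.95 applied to every factor, and at 1.3 the planned model stays at 4.7–6.5%. The primary estimate of hardship incidence is not affected.

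**What to change.** Add two or three sentences to Section 7.2:

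- Keep the planned linear model. Prespecify beside it one that adds the eight baseline covariates of the Cox model (age, race, marital status, employment, income, insurance status, education, gender), plus baseline Zubrod performance status if it is recorded then. Section 6.5 does not say when it is graded. Do not use a month-3 value. Report both models.
- For the logistic check, define decline and fix a short covariate list before the data are seen, for example 3-month HRQOL, age, income and employment. With hardship that makes five terms, or 50 events at the plan's 10:1 ratio, against 53–96 in the illustration. State in advance which term is dropped first if missed forms leave fewer events.
- State that the adjustment addresses measured demographic confounding only, that confounding by prognosis largely remains, and that the result is an exploratory association.

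Cost: about 9–12 degrees of freedom out of at most about 235 patients. In simulation A the standard error of the hardship coefficient rises 0.4–5%, or up to 8% if 25% have hardship by month 3. The estimate may move away from zero where confounders cancel, which is one reason to show both models. The eight covariates are already needed for the Cox model, so no new data collection is required for them.
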